8.3.6 Laboratory Data

Schedule and parameters

- Hematology, biochemistry, urinalysis, urine drug screen, fasting serum C-peptide, and serology test will be performed at screening visit only
- Urine cotinine and urine β -HCG (for females with childbearing potential) will be measured at screening visit, at visits 2, 6, 9, 12, 15 and 16 in the titration period, and at visits 19, 22, 25, 28 and 29 in the extension period, as well as the early termination visits in both study periods.

- HbA1c will be measured at screening visit and at end of treatment visit/early termination visit in both study periods

List of Hematology and Chemistry Laboratory Tests

Biochemistry						
Hematology	Plasma/serum electrolytes	Metabolism	Liver Status	Kidney Status	Specialty Tests	Serology
Hemoglobin	Sodium	Albumin	Total and conjugated bilirubin	Blood Urea nitrogen (BUN)	HbA _{1c}	Hepatitis B antigen
Hematocrit	Potassium	Total Protein	Alkaline phosphatase	Creatinine Uric acid	Fasting serum C-peptide	Hepatitis C antibodies
Red blood cells	Chloride	Total cholesterol	Alanine aminotransferase			anti-HIV-1 and anti-HIV-2 antibodies
White blood cells with differential	Calcium	Low-density lipoprotein	Aspartate aminotransferase			
Neutrophils	Phosphorus	Triglycerides				
Lymphocytes	Carbon dioxide					
Monocytes						
Eosinophils						
Basophils						
Platelets						

Urinary Laboratory Tests

Urinalysis	Specialty tests	Urine Drug Screen
Albumin/creatinine ratio	Urine pregnancy test ^a	Amphetamines/methamphetamines
Ketones	Cotinine	Benzodiazepines
Glucose		Cannabinoids
Erythrocytes		Benzoylcegonine
Leukocytes		Opiates
pH		Barbiturates
Urobilinogen		
Nitrates		
Specific gravity		

a: Only for women of childbearing potential

Table presentation

For HbA1c:

Value and change from baseline will be summarized by cohort and analysis visit.

For fasting serum C-peptide:

Value at screening visit will be summarized by cohort, and presented as part of the ‘Demographics and baseline characteristics’ table.

Subject Listings

The results of all lab measurements, including hematology, biochemistry, urinalysis, HbA1c, fasting serum C-peptide, serology, urine drug screen, urine cotinine, and urine pregnancy test, will be listed, by parameter and by (in the order of) cohort, investigator site, subject and visit.

Graphical Presentation

For HbA1c, a Mean (SE) plot representing mean and SE for each cohort at each analysis visit will be provided.

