STATISTICAL CONSIDERATIONS	
Sample size determination:
 
Sample size calculation is based on a total standard deviation (SD_{Total}) of 0.725 for the log-transformed apparent total body clearance (CL/F). The sample size is planned to target the maximum imprecision of the 95% confidence interval for the geometric mean estimates of CL/F in each age cohort within 40%, with at least 80% power.
 
A sample size of 14 subjects in the first cohort will provide at least 80% power in order to target the maximum imprecision of the 95% confidence interval of the geometric mean estimates within 40%, assuming an SD_{Total} of 0.725 as the most conservative approach. For Cohort 2 and Cohort 3, the sample size may be adjusted to enable taking the PK variability in previous cohorts into account.
 
Analysis population:
 
All subjects in the clinical study who receive a dose of

	
AFREZZA will be included in the safety population.
 
All subjects without any major deviations related to study drug administration (no sneezing or coughing right after AFREZZA inhalation on Day 1), and for whom any PK parameters are available, will be included in the PK population.
 
Pharmacokinetic analysis:
 
All analyses will be performed in a descriptive manner based on the PK population.
 
Safety analyses:
 
Analyses will be performed in a descriptive manner by age cohort.
 
The safety analysis will be conducted on the safety population and will be based on the review of the individual values (clinically significant abnormalities) and descriptive statistics (summary tables and plots if appropriate). Individual values will be flagged for potentially clinically significant abnormalities and treatment-emergent adverse events will be tabulated (counts and percent). The details of the analyses for the study will be specified in the Statistics and Analysis Plan (SAP) for the study.

DURATION OF STUDY PERIOD (per subject)	The total duration of the study will be approximately 6 to 8 weeks per subject through the 4-week titration period.
STUDY COMMITTEES	Data Monitoring Committee: an independent group of experts will be responsible for monitoring the safety of the subjects enrolled in the clinical trial on an on-going basis in order to provide, in a timely fashion, appropriate recommendations to the Sponsor.

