9.2.4 Safety assessment during the study

Safety assessments during the study will be done according to the Flow Chart 1.1 and will include, but is not limited to:

- Physical examination: the abbreviated physical examinations will include, but not limited to, general appearance, mental status, respiratory and cardiovascular systems, and other evaluations deemed appropriate by the Investigator for safety reasons
- Body weight (kg)
- Vital signs (respiratory rate, sitting blood pressure, and pulse measurements) will be recorded after the subject has been sitting for 5 minutes
- Laboratory tests:
 - Urine pregnancy test: females of childbearing potential
 - Urine cotinine
- Adverse events spontaneously reported by the subject or observed by the Investigator will be monitored
- FEV₁ testing: Spirometry will be done to assess pulmonary function. Another pulmonary function test may be done after the consultation of a pediatric pulmonologist if the subject is unable to perform spirometry
- Concomitant medications reported by the subject or by the Investigator will be recorded

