10.2.5 Cough

Cough as an isolated symptom will be reported as an AE in the e-CRF. For cough associated with a defined clinical entity (e.g., upper respiratory tract infection), the appropriate diagnosis associated with the cough will be recorded in the AE e-CRF.

10.3 OBLIGATION OF THE INVESTIGATOR REGARDING SAFETY REPORTING**10.3.1 General guidelines for reporting adverse events**

All AEs, regardless of seriousness or relationship to IMP/NIMP, occurring between consent/assent and the end of the study will be recorded.

AEs are to be recorded as defined by the protocol on the corresponding e-CRF for subjects who are enrolled and for those who fail screening.

For screen failed subjects, recording in the e-CRF is only performed in case of an SAE occurring during the screening period or in case of an AE when some study-specific screening procedures expose the subject to safety risks. Whenever possible, diagnosis or syndrome should be reported instead of individual associated symptoms (e.g., record “Influenza” not fever, chills, etc). The Investigator should specify the date of onset, intensity (see definitions in Section 10.2.1), action taken with respect to IMP/NIMP, corrective treatment/therapy given, additional investigations performed, outcome, and Investigator’s opinion as to whether there is a reasonable possibility that the AE was caused by the IMP/NIMP.

In order to ensure the safety of the subjects, the Investigator should take appropriate measures to follow all AEs until clinical recovery is complete and laboratory results have returned to normal, or until no further improvement is expected, or until death. Follow-up of the AE resolution/status will end at the follow-up visit. If necessary, SAEs will be followed beyond the last planned visit per protocol until resolution, no further improvement is expected, or death. Additional investigations of the SAE may be requested by the Sponsor.

When treatment is prematurely discontinued, an early termination (ET) visit should be conducted as soon as possible. Laboratory, vital sign, or electrocardiogram abnormalities are to be recorded as AEs only if:

- Laboratory and/or vital signs not specifically addressed elsewhere in the protocol change $\geq 10 \times$ the upper or the lower limits of normal and are undesired, and are a change from the pre-enrollment assessment values, and/or
- Are symptomatic, and/or

- Are clinically significant

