13.4.3 Baseline safety parameters

Safety parameters will be summarized in a descriptive manner for the included subjects.

Baseline for safety parameters will be defined as the last available and evaluable parameter value before and closest to the first IMP dosing for laboratory data, and for vital sign parameters, including body temperature and further safety parameters unless specified differently.

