4.2 Safety Endpoints

- Adverse events, serious adverse events, treatment-emergent adverse events
- Adverse Events of Special Interest (AESI), which include the following events:
 - Acute bronchospasm
 - Verified Clinically relevant decline in pulmonary function
 - Hypersensitivity reactions, including anaphylaxis, which can occur with insulin products, including AFREZZA[®]
 - Diabetic ketoacidosis
- Vital sign measurements

Version Date: 17-Jan-2020

- Abnormal clinical laboratory assessments
- Hypoglycemia: asymptomatic, symptomatic, nocturnal, and severe hypoglycemia according to the 2014 International Society for Pediatric and Adolescent Diabetes guideline (3)
- Anti-insulin antibodies

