For percentage calculation, number of subjects in each cohort in the safety population will be used as denominator for the summaries for the entire study and the titration period. For the extension period, number of subjects in safety population who participate in extension period (see definition in Section 5.4) will be used as denominator.

Observation time for TEAE is defined as:

Version Date: 17-Jan-2020

- For the entire study: min(last visit/contact date, last dose date +30) – Study Day 1 + 1
- For the titration period:
 - min(last visit/contact date, last dose date +30) – Study Day 1 + 1, for subjects who do not participate in the extension period
 - date of Visit 15 – Study Day 1 +1, for subjects who participate in the extension study
- For the extension period: min(last visit/contact date, last dose date +30) – date of Visit 15, for subjects who participate in the extension period only.

Subject Listing

Individual data listings will be provided for the following, by (in the order of) cohort, investigator site and subject:

- All adverse events
- Treatment emergent adverse events
- Prior adverse events and follow-up adverse events
- Serious treatment-emergent adverse events
- Treatment-emergent adverse events leading to discontinuation from the trial
- Treatment-emergent adverse events leading to death
- Treatment-emergent adverse events leading to temporary treatment interruption
- Treatment-emergent adverse events of special interest

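### Does a laboratory safety endpoint need changing when hematology, biochemistry and urinalysis are drawn only at screening?

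*SAP*

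**What the plan says.** Both documents carry the same endpoint line, "Abnormal clinical laboratory assessments" (protocol synopsis, safety endpoints; SAP 4.2). Neither says which tests it covers, what counts as abnormal, or at which visits.

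On the schedule, SAP 8.3.6 says: "Hematology, biochemistry, urinalysis, urine drug screen, fasting serum C-peptide, and serology test will be performed at screening visit only". The protocol's flow chart 1.1 agrees: the row for the three panels has a single mark, under Screening. Protocol 9.2.4 names two laboratory tests during the study, urine cotinine and "Urine pregnancy test: females of childbearing potential", in a list that is expressly open-ended.

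On analysis, the synopsis says "Individual values will be flagged for potentially clinically significant abnormalities" and leaves the details to the SAP. Protocol 13.4.3 sets a baseline, "the last available and evaluable parameter value before and closest to the first IMP dosing for laboratory data". Protocol 13.8 rests the safety evaluation on review of individual values for clinical significance plus descriptive statistics, all on the safety population. SAP 8.3.6 plans tables for HbA1c and C-peptide and listings for everything else: "The results of all lab measurements, including hematology, biochemistry, urinalysis" and the remaining tests are to be listed by cohort, site, subject and visit.

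Protocol 10.3.1 governs abnormalities that arise on study: "Laboratory, vital sign, or electrocardiogram abnormalities are to be recorded as AEs only if" one of a set of conditions is met. These include a very large departure from the normal limits, symptoms, clinical significance, a need for treatment or further work-up, an effect on dosing, or meeting the SAE or AESI definition.

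**The concern.** Safety and tolerability in children aged 4 to 17 is the first objective, and protocol 4.4 states that safety has not been evaluated in children. A reader who sees a laboratory endpoint, a defined laboratory baseline and a promise to flag abnormal values will expect a comparison of values before and after treatment. For hematology, biochemistry and urinalysis there is nothing scheduled to compare.

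The AE route does not fully replace it. A laboratory abnormality recorded as an AE would be reported as a percentage for which "number of subjects in each cohort in the safety population will be used as denominator": 18, 14 and 14 planned subjects, whether or not they were tested. One such event would read as 1/18 = 5.6% or 1/14 = 7.1%. A count of zero would not show that values had stayed normal, because nobody is scheduled to be retested. If the study report treated that zero as laboratory reassurance, it would claim more than the data hold.

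**Working it through.** The plan states no figure on this point, so there is none to reproduce. The check is a count of what is collected and reported, followed by what each possible change would buy.

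**1. Scheduled post-dose values in the three panels.** Flow chart 1.1 and SAP 8.3.6 give one draw at screening and none later. Over the planned sample: 3 panels × 0 post-dose visits × 46 subjects = 0. The 52-week extension described in the SAP does not alter this, since its screening-only rule adds no draw for these panels there either.

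**2. Laboratory tests that do have post-dose values.** For a subject who completes titration:

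- HbA1c: 1 (Visit 15)
- Urine cotinine: 5 (Visits 6, 9, 12, 15, 16; the Visit 2 test precedes dosing)
- Urine β-HCG, females of childbearing potential: 5 (same visits)
- Day 1 glucose: 6 (G01 to G06), reported under PK
- Anti-insulin antibody: 1, which is its own endpoint

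The endpoint is therefore not empty.

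**3. Planned outputs (SAP Appendix 3).** Tables: 6 (14.1.1) + 9 (14.1.2) + 5 (14.2) + 20 (14.3) + 5 (14.4) = 45. None is devoted to the three panels. TEAE tables: 14.3.1.1 to 14.3.1.12 gives 12, plus 14.3.1.2.1, making 13; any of these could count an abnormality recorded as an AE. The panels have three listings (16.2.4.5 to 16.2.4.7), placed among the baseline measurements and each titled as results at screening.

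**4. Does the endpoint line contradict the schedule?** Only if it is read as covering change from baseline in these three panels. The line names no panel and mentions neither change nor treatment emergence. Read with protocol 10.3.1 and 13.8, it means that abnormal results, when they occur, are reviewed individually and become AEs if they meet the stated conditions. That is a workable reading for a small descriptive study, and every part of it can be carried out.

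**5. What a repeat draw would buy.** Assume one post-dose sample in every planned subject. With zero new abnormalities, the exact one-sided 95% upper bound on the true rate is 1 − 0.05^(1/n). The chance of seeing at least one case at true rate p is 1 − (1 − p)^n. The 5% and 10% rates are illustrative; the documents give none.

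| n | Upper bound if zero seen | Chance of ≥1, p = 5% | Chance of ≥1, p = 10% |
|---|---|---|---|
| 14 | 19.3% | 0.51 | 0.77 |
| 18 | 15.3% | 0.60 | 0.85 |
| 46 | 6.3% | 0.91 | 0.99 |

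The cost is further blood from children who already give (14 + 5) samples × 2 mL = 38 mL for insulin and FDKP on Day 1 (protocol Tables 3 and 4). Panel volumes are not stated. Protocol Table 1 uses none of these panels to assess or mitigate a listed risk.

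**6. What rewording would buy.** Replacing the line with a list of the repeated tests changes no data and no output, and it can introduce conflicts. Day 1 glucose is summarized on the PK population (Table 14.2.3.1), which excludes subjects who cough or sneeze right after inhalation, whereas protocol 13.8 puts all safety analyses on the safety population. A closed list would also drop an unscheduled abnormal hematology or biochemistry result from the endpoint, which is the case one would most want to keep.

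**The case for a change.** The best argument for a change comes from the SAP's own practice. ECG is also recorded at screening only; it is filed with the baseline measurements and does not appear as a safety endpoint in SAP 4.2. The three panels have the same schedule and the same filing, yet an unqualified laboratory line stands among the endpoints. Where the plan does want an on-study comparison, it defines one. FEV₁ decline has a threshold (more than 15% below baseline) and a denominator of subjects attending the visit. Anti-insulin antibody has a shift table restricted to subjects with both assessments. The laboratory endpoint has neither, and the SAP text does not supply the flag criterion that the synopsis leads one to expect.

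Much of this stands as fact. The line is loosely worded, the SAP text gives no laboratory flag limit, and scheduled data cannot show change in these panels. What does not stand is that something must be altered as a result. The missing flag criterion may sit in the table and listing shells, which are separate files (SAP Appendix 4) and cannot be checked here; if it does not, an analyst can set a convention before the listings are run. A denominator of all safety subjects is the normal convention for AE tables and is not particular to laboratory events. The comparison with ECG shows an uneven habit of drafting, not an analysis that will go wrong.

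**Conclusion.** No change is needed. The observation is correct in its facts: zero scheduled post-dose hematology, biochemistry or urinalysis values across 46 planned subjects, no dedicated table among 45, and no laboratory flag limit in the SAP text. The consequence is small. The protocol and SAP agree on the screening-only schedule, SAP 8.3.6 states it openly, and the three listing titles repeat it, so a reader of the outputs is unlikely to mistake baseline results for on-treatment ones. Abnormalities that come to light on study have a route through protocol 10.3.1 and the TEAE tables.

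A wording change would alter no test, analysis, result or conclusion. A repeat draw would, but it trades further blood sampling in children for limited information: even with no abnormality seen, upper bounds of 15.3% to 19.3% by cohort and 6.3% overall. The screening-only schedule is a fair choice for the sponsor to make.

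This rests on three assumptions: that the endpoint line is read together with protocol 10.3.1 and 13.8; that the shells or a listing convention supply any flag used; and that the study report draws no conclusion about on-treatment change in these panels from an absence of laboratory AEs.

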8.3.7 Vital Signs

Schedule and Parameters

Version Date: 17-Jan-2020

Vital signs assessments will be made at screening, at visits 2, 6, 9, 12, 15 and 16 in the titration period, and at visits 19, 22, 25, 28 and 29 in the extension period, as well as at the early termination visits in both periods. Height will be collected at screening only. The following parameters will be collected at all visits: respiratory rate, sitting blood pressure (systolic blood pressure and diastolic blood pressure), pulse rate, temperature, and body weight. At Visit 2, these parameters will be collected at two time points: pre-dose and post-dose.

All the measurements will be presented in international units. If measurements are collected in different units, a conversion will be made first before presentation. Below is the summary of conversion between different units.

Conversion	Formula
From lbs to kg in weight	Weight (kg) = Weight (lbs) x 0.45
From inch to meter in length	Length (meter) = Length (inch) x 2.5
From F to C in temperature	Temp (C) = {Temp (F) -32} x 5/9

Table presentation

For each parameter, descriptive statistics will be provided by cohort and analysis visit/time point. Change from baseline to all post-baseline visits/time points will be provided by cohort, except for height.

Subject Listings

Detailed information of every measurement will be listed, by (in the order of) cohort, investigator site, subject and visit/time point.

Graphical Presentation

For BMI, a Mean (SE) plot representing mean and SE for each cohort at each analysis visit will be provided.

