9.2 SAFETY

9.2.1 Baseline demographic characteristics

Baseline demographic characteristics at screening will consist of:

1. Age (years)
2. Height (cm): should be measured when the subject's shoes are off, feet together, and arms by the sides. Heels, buttocks, and upper back should also be in contact with the wall when the measurement is made.
3. Body weight (kg): should be obtained with the subject wearing undergarments or very light clothing and no shoes, and with an empty bladder. The floor surface on which the scale rests must be hard and should not be carpeted or covered with other soft material. The same scale should be used throughout the study, and calibrated on a regular basis as recommended by the manufacturer.
4. Body mass index
5. Race and/or ethnicity
6. Gender

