5.10 BMI

BMI at a given visit will be calculated as

Weight (in kg) measured at this visit/height (in m) measured at screening ².

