8 STATISTICAL METHODS

8.1 General Considerations

In this study, unless otherwise specified, all analyses will be performed in a descriptive manner by age cohort (including ‘Cohort 1’, ‘Cohort 2’, ‘Cohort 3’ and ‘Total’). The ‘Total’ group will include all subjects in the analysis population.

Where appropriate, all dimensions will be summarized in metric units, but listings will, in addition, represent values as collected.

For continuous variables, the number of subjects, mean, standard deviation, median, minimum, and maximum values will be displayed, as appropriate according to the type of data. The minimum and maximum will be displayed to the same number of decimal places that the data were recorded to. The mean and median will have 1 extra decimal place and the standard deviation will have 2 extra decimal places. The geometric mean and coefficient of variation (CV) will have 2 extra decimal places. Confidence interval (of the mean) will have the same decimal precisions as the mean.

For categorical variables, frequency counts and percentages of total for each category will be presented; missing values will be treated as a separate category, where appropriate. Percentage will be presented in 1 decimal place.

Visit specific data (e.g., 7-point SMBG or pulmonary function tests) will be summarized by analysis visit, which is defined based on the visit windows specified in Section 0

Non-visit specific data (e.g., hypoglycemic events or daily dose) will be summarized by study period and/or by time interval. See relevant sections for more details.

8.1.1 **Data Handling/Imputation Methods**

8.1.1.1 **Missing Data Imputation**

Unless otherwise specified, missing data other than start date of adverse events (AE) or start/end date of concomitant medications (CM) will not be imputed.

The imputation rules for start date of Aes and start/end date of CMs are as follows:

Adverse Events

- Start date
 - If the start date is completely missing, the start date is set to the date of first dose.
 - If the year is present and the month and day are missing or the year and day are present and the month is missing:

If year = year of first dose, then set month and day to month and day of first dose

Version Date: 17-Jan-2020

- If year < year of first dose, then set month and day to December 31.
- If year > year of first dose, then set month and day to January 1st.
- If the month and year are present and the day is missing:
 - If year = year of first dose and

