Summary tables will be reported by cohort and study period (titration period, extension period, and entire study). Only hypoglycemic events occurred on treatment (i.e., with start date between the first dose date and last dose date, both inclusive) will be included. Number and percentage of subjects with hypoglycemic events, number of hypoglycemic events, and event rate in subject-month accounting for observation time will be presented for the following categories:

- All hypoglycemic events
- Asymptomatic hypoglycemic events
- Symptomatic hypoglycemic events
- Nocturnal hypoglycemic events
- Severe hypoglycemic events
- Documented hypoglycemic events
- Symptomatic documented hypoglycemic events
- Asymptomatic documented hypoglycemic events

For percentage calculation, number of subjects in each cohort in the safety population will be used as denominator for the summaries for the entire study and the titration period. For the extension period, number of subjects in safety population who participate in extension period will be used as denominator.

For calculation of event rate, observation time is defined as treatment exposure time (total exposure time and period-specific exposure time for the corresponding analysis respectively, see definition in Section 5.5).

In addition, causality of hypoglycemic events will be summarized (for the entire study only). Number and percentage of subjects experiencing hypoglycemic events in each causality category will be presented by cohort.

Graphical Presentation

Only hypoglycemic events occurred on treatment will be included. The following graphs will be presented by cohort and overall:

- Day profile of hypoglycemic events

Event rate (in subject-month) will be calculated at 1 week interval for the titration period and at 1 month interval the extension period, and plotted against time since the start of the study period. Onset date of the event will be used to determine the time interval. Weeks since the start of the study period will be calculated as $\text{int}((\text{date} - \text{start date of the study period} + 1) / 7)$. Months since the start of the period will be calculated as $\text{int}((\text{date} - \text{start date of the study period} + 1) / 30.4375)$.

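### Three SAP derivation rules give wrong results if programmed as printed: the inch and pound conversions, the week/month index, and the post-dose hour bins

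*SAP*

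**What the plan says.** **Unit conversions (SAP 8.3.7).** The table gives "Length (meter) = Length (inch) x 2.5" and "Weight (kg) = Weight (lbs) x 0.45". It applies when data arrive in other units: "If measurements are collected in different units, a conversion will be made first before presentation". SAP 8.1 adds "Where appropriate, all dimensions will be summarized in metric units". SAP 5.10 then computes BMI as "Weight (in kg) measured at this visit/height (in m) measured at screening", with height squared. Protocol 9.2.1 plans height in cm ("Height (cm): should be measured when the") and weight in kg.

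**Week and month index (SAP 8.3.3, day profile).** "Event rate (in subject-month) will be calculated at 1 week interval for the titration period"; monthly intervals are used for the extension. "Weeks since the start of the study period will be calculated as" int((date − start + 1)/7), and months use the same form with 30.4375. The last intervals are named Week 4 and Month 12, and each runs on to the end of treatment. The hypoglycaemia time profile is also split by week and month, and SAP 8.3.4 builds the cough profile the same way.

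**Hour bins (SAP 8.3.3, time profile).** The bins are printed as [0,1], (1,2), (2,3) and (3,4) hours after the pre-meal dose. Events within 4 hours of that dose are to be included.

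**The concern.** Each rule is a programming instruction, and each fails if followed exactly.

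- **Conversions.** An inch is 0.0254 m, so the length rule cannot return metres, and 0.45 is a coarse pound factor. A literal metre error would be seen at once. The likelier silent failure is a programmer treating 2.5 as centimetres per inch, which leaves plausible but biased heights and BMIs. Mixing converted and metric records would create false differences between subjects. If one subject's weights were recorded in different units at different visits, it would also create a false change from baseline.
- **Week index.** The numerator is already the 1-based relative day of SAP 5.3. Truncating it after division moves every boundary one day early and creates an interval 0. The SAP text does not say whether the index or the index plus one is the label, so two programmers could draw different figures.
- **Hour bins.** Open ends leave exact hours in no bin. The 2 h gap is the one most likely to lose events, because the scheduled post-dose glucose check opens at 120 minutes (Protocol 9.2.6.2) and a reading below 70 mg/dL alone counts as an event (SAP 8.3.3).

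The outputs concerned are the hypoglycaemia day and time profiles and the cough profile (Figures 14.3.1.1, 14.3.1.2, 14.3.2.1). For any non-metric record, they also include the demographics table (14.1.1.3), the vital signs table (14.3.3.1) and the BMI plot (Figure 14.4.2.1).

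**Working it through.** **1. Conversions.** Inputs: printed factors 2.5 and 0.45 (SAP 8.3.7); true factors 0.0254 m/in and 0.453592 kg/lb; BMI = kg/m² (SAP 5.10).

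- Length as metres: 2.5/0.0254 = 98.4 times too large.
- Length read as centimetres: 2.5/2.54 − 1 = −1.57%.
- Weight: 0.45/0.453592 − 1 = −0.79%. At 130 lb this is 58.5 kg instead of 58.97 kg, a difference of −0.47 kg.
- The temperature formula in the same table is correct.

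Example record, 64 in and 130 lb:

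| Reading | Calculation | BMI | Error |
|---|---|---|---|
| Correct | 58.97/1.6256² | 22.31 | – |
| Literal, both converted | 58.5/160² | 0.0023 | about 10,000-fold too small |
| 2.5 as cm, both converted | 58.5/1.60² | 22.85 | +2.4% |
| 2.5 as cm, height only | 58.97/1.60² | 23.03 | +3.2% |
| Weight only converted | 58.5/1.6256² | 22.14 | −0.8% |

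**2. Week index.** With day = date − start + 1, the printed rule is int(day/7). Treatment is taken to Day 29, the target day of Visit 15. The comparison is min(int((day − 1)/7) + 1, 4), which gives full weeks ending in Week 4.

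| Printed index | Days | Length | Intended week and days |
|---|---|---|---|
| 0 | 1–6 | 6 | Week 1: 1–7 |
| 1 | 7–13 | 7 | Week 2: 8–14 |
| 2 | 14–20 | 7 | Week 3: 15–21 |
| 3 | 21–27 | 7 | Week 4: 22–29 |
| 4 | 28–29 | 2 | (part of Week 4) |

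- Label = index + 1, capped at 4: Days 7, 14 and 21 are in the wrong week, 3 of 29.
- Label = index: only Days 7, 14, 21, 28 and 29 carry the right number, so 29 − 5 = 24 of 29 are wrong.

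Week 4 exposure for 14 subjects all treated to Day 29 (assumption):

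- Index + 1 (Days 21–29): 14 × 9/30.4375 = 4.14 subject-months.
- Index as label (Days 28–29): 14 × 2/30.4375 = 0.92.
- Intended (Days 22–29): 14 × 8/30.4375 = 3.68.

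The SAP takes each rate's denominator from the days in the same interval. Each rate is therefore valid for its own bin; the boundaries and labels are what is wrong.

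**Months.** With int(day/30.4375), index 11 starts on Day 335 of the extension and index 12 on Day 366. So Month 12 starts on Day 335 (index + 1) or Day 366 (index as label), against Day 336 under int((day − 1)/30.4375) + 1. Under the index label it would hold a single day if treatment ran to Day 366.

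**3. Hour bins.** Testing every whole minute from 0 to 240 against the printed bins leaves 120, 180 and 240 in no bin. Minute 60 is covered by [0,1], and no minute is counted twice.

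**The case against.** The strongest objection is that little depends on this. Every affected output is descriptive. None of the four figures is marked for the DMC package in SAP Appendix 3, whereas the listings of hypoglycaemic events and cough are, so individual events remain visible. The main hypoglycaemia table uses exposure over the whole period. That is right, and it limits the weight of the point; it does not make the formulas correct.

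On conversions, the protocol asks for cm and kg, and no document shows that any inch or pound record exists. The literal inch error would be caught on sight, and 0.45 is coarse rounding rather than a unit mistake. All of this stands. But the SAP expressly provides for other units, the trial is run in the United States, and the vital signs and demographics tables do go to the DMC.

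On weeks, a zero-based elapsed count is an ordinary plot axis, and the figure shells, which are separate files not supplied, may fix the labels. The 24-day figure is therefore the less favourable reading. Even on the more favourable one, the first week has six days and three days are misplaced, and a count of elapsed full weeks would not add 1 before dividing. Visit 15 also has a ±1 day window, so the length of the last bin will vary.

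On hour bins, the point rests on bracket types in text extracted from a PDF. They should be confirmed in the source file. The first bin's closed brackets did come through, and as printed the gaps are there.

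The month index matters only if the SAP's 52-week extension, which is not in the current protocol's design, is analysed.

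**Conclusion.** The concern holds: all three rules are wrong as printed.

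- **Conversions:** no effect on records in cm and kg. For other records, height is 98.4 times too large, or 1.6% low on the centimetre reading; weight is 0.8% low; and BMI is unusable, or 2.4% to 3.2% high on the centimetre reading when height is converted. How many such records exist is not stated.
- **Week index:** 3 or 24 of 29 days misassigned, depending on the label, assuming treatment to Day 29.
- **Hour bins:** three exact times unassigned, subject to confirming the brackets in the source file. The number of events lost cannot be known from the documents.

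The consequences are confined to descriptive safety and baseline displays. No hypothesis test, PK endpoint, main event table or cohort-progression rule depends on these formulas. The correction is worth making because the SAP governs the programming of paediatric safety displays and, as written, does not produce the intervals it names.

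**What to change.** Amend SAP 8.3.7 and 8.3.3 as follows; 8.3.4 follows automatically.

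- Length (m) = inches × 0.0254; weight (kg) = pounds × 0.4536.
- Week = int((date − start)/7) + 1, capped at 4, so Week 1 is Days 1–7 and Week 4 is Day 22 to the end of treatment.
- Month = int((date − start)/30.4375) + 1, capped at 12, if the extension is analysed.
- State that these values are the interval labels, and check that the figure shells agree.
- Hour bins [0,1], (1,2], (2,3], (3,4], which assign every time from 0 to 4 h exactly once.

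The rule that takes observation time from days within the interval can stay. The cost is SAP wording and a few lines of code; no new data are needed.
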